# APPENDIX 2 MISSING AND PARTIAL RADIOTHERAPY AND SURGERY DATES IMPUTATION ALGORITHMS

### **Procedures – Imputation Rules.**

If reported procedure start date is a full valid date then set start date equal to the date part of procedure start date.

In case of partial date use imputation rules described below:

- If only day is missing then
  - If month and year of procedure match month and year of first dose date then impute as date of first dose;
  - If month and year of procedure don't match month and year of first dose date then impute as first day of that month and year.
- If both day and month are missing, then impute as maximum between 01JAN of the year and date of the first dose;
- If date is completely missing or invalid then leave missing.

Note: Imputation is not applicable to data where start date is not collected (for example "PRIOR RADIOTHERAPY" CRF). Set start date to missing in this case.

If reported end date is a full valid date then set end date equal to the date part of the reported end date.

In case of partial date use imputation rules described below:

- If reported end date is partial then set end date equal to the last possible reported end date based on the partial entered reported end date.
- If reported end date is missing, continuing, unknown or invalid then set end date equal to the most recent database extraction date.

If end date was imputed then compare end date to the death date or last known alive date if subject is not dead. If posterior then end date should be imputed to death date (or last known alive date if subject not dead).

Note: Imputation of partial dates only applies to data entered on "RADIOTHERAPY" CRF page. For other CRF pages in case of partial dates set end date to missing.

#### **Surgeries – Imputation Rules.**

If reported surgery date is a full valid date then set start date equal to the date part of surgery date.

In case of partial date, use one of the two imputation rules described below:

A. For data collected on "PRIOR SURGERY RELATED TO CANCER" CRF page:

- If only day is missing then impute as the first day of the month;
- If both day and month are missing then then impute as 01JAN of the year;
- If date is completely missing or invalid then leave missing.

- B. For data collected on other CRF pages (deemed to be on-treatment/subsequent surgeries):
- If only day is missing then
  - If month and year of surgery match month and year of first dose date then impute the missing date as the date of first dose;
  - If month and year of surgery don't match month and year of first dose date then impute as first day of that month and year;
- If both day and month are missing then impute as maximum between 01JAN of the year and date of the first dose;
- If date is completely missing or invalid then leave missing.

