8.3.2 Secondary Endpoints

Overall survival (OS) in randomized participants with PD-L1 CPS ≥ 1 . OS is defined the same way as for the primary endpoints.

PFS is defined as the time from randomization to disease progression, using RECIST 1.1 criteria, or, if there is no documented progression, death. (The date of progression will be based on the BICR assessment of progression). Participants who neither progress nor die will be censored on the date of their last tumor assessment. Participants who receive subsequent anti-cancer therapy prior to documented progression, including tumor-directed radiotherapy and tumor-directed surgery, will have their PFS time censored on the date of their last tumor assessment prior to subsequent therapy.

The Objective Response Rate (ORR) is defined as the number of participants with a best overall response (BOR) of complete response (CR) or partial response (PR), divided by the number randomized in the population.

The BOR is defined as the best response, based on RECIST 1.1 criteria, recorded between randomization and either progression or subsequent anticancer therapy (including tumor-directed radiotherapy and tumor-directed surgery), whichever occurs first. (The BOR will be based on BICR assessments). For participants without evidence of RECIST 1.1 progression or subsequent anticancer therapy, all available tumor evaluations will contribute to the BOR assessment.

Duration of objective response (DOR) is the time between the first documented response (CR or PR) and progression, per RECIST 1.1, or, if no progression is reported, death. The DOR of a participant who neither progresses nor dies will be censored as in the primary definition of PFS. DOR is calculated on the subset of participants whose best response was either CR or PR, according to BICR assessments.

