# 4.2.2.1 Primary Definition of Progression-Free Survival (Accounting for Subsequent Therapy)

[figure not shown]
The primary definition of PFS (PFS truncated at subsequent therapy) is defined as the time between the date of randomization and the date of first documented tumor progression, based on BICR assessments (per RECIST v1.1 criteria), or death due to any cause, whichever occurs first. Figure 4.2.2.1-1 show the graphic display of primary definition of PFS.

Subjects who die without a reported progression will be considered to have progressed on the date of their death. The following censoring rules will be applied for the primary definition of PFS:

- Subjects who did not progress or die will be censored on the date of their last evaluable tumor assessment.
- Subjects who did not have any on study tumor assessments and did not die will be censored on their date of randomization.
- Subjects who receive subsequent anti-cancer therapy prior to documented progression will be censored at the date of the last evaluable tumor assessment conducted on or prior to the date of initiation of the subsequent anti-cancer therapy.
- Subjects who did not have a documented progression and received subsequent anti-cancer therapy will be censored at the date of the last evaluable tumor assessment conducted on or prior to the initiation of the subsequent anti-cancer therapy.

Censoring rules for the primary definition of PFS (PFS truncated at subsequent therapy) are presented as follows and in Table 4.2.2.1-1.

Figure 4.2.2.1-1: PFS Primary Definition

**Table 4.2.2.1-1:** Censoring Scheme Used in Primary Definition of PFS

Situation	Date of Progression or Censoring	Outcome
No baseline tumor assessments*	Date of randomization	Censored
No on study tumor assessments and no death*	Date of randomization	Censored
Subsequent anti-cancer therapy started without death or progression per RECIST v1.1 reported prior or on the same day	Date of last evaluable tumor assess- ment prior to or on the date of initi- ation of the subsequent anti-cancer therapy	Censored
Documented progression per RE- CIST v1.1 and no new anti-cancer started before	Date of the first documented pro- gression per RECIST v1.1 (excludes clinical progression)	Progressed
No progression and no death, and no new anti-cancer therapy started	Date of last evaluable tumor assessment	Censored
Death without progression per RE- CIST v1.1 and no new anti-cancer started before	Date of death	Progressed

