\* Tumor assessments and death if any, occurring after start of subsequent anti-cancer therapy are not considered.

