#### 8 CONVENTIONS

The following conventions may be used for imputing partial dates for analyses requiring dates:

- For missing and partial adverse event onset dates, imputation will be performed using the Adverse Event Domain Requirements Specification
- For missing and partial adverse event resolution dates, imputation will be performed as follows (these conventions may change):
  - If only the day of the month is missing, the last day of the month will be used to replace the missing day. If the imputed date is after the death date or the last known alive date, then the latest known alive date or death date is considered as the resolution date.
  - If the day and month are missing or a date is completely missing, it will be considered as missing.
- Missing and partial non-study medication domain dates will be imputed using the derivation algorithm described in 4.1.3 of BMS Non-Study Medication Domain Requirements Specification.
- Missing and partial radiotherapy and surgery dates will be imputed using algorithm described in APPENDIX 2.
- For death dates, the following conventions will be used for imputing partial dates:
  - If only the day of the month is missing, the 1st of the month will be used to replace the missing day. The imputed date will be compared to the last known alive date and the maximum will be considered as the death date.
  - If the month or the year is missing, the death date will be imputed as the last known alive date.
  - If the date is completely missing but the reason for death is present, the death date will be imputed as the last known date alive.
- For date of progression after start of study therapy, the following conventions will be used for imputing partial dates:
  - If only the day of the month is missing, the 1st of the month will be used to replace the missing day. In case of the date of death is present and complete, the imputed progression date will be compared to the date of death. The minimum of the imputed progression date and date of death will be considered as the date of progression.
  - If the day and month are missing or a date is completely missing, it will be considered as missing.

- For date of progression to prior therapies, the following conventions will be used for imputing partial dates:
  - If only the day of the month is missing, the 1st of the month will be used to replace the missing day.

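### Partial start dates of subsequent radiotherapy or surgery are set to the earliest possible day, so a documented progression can become an earlier censoring in primary-definition PFS and in DOR

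*SAP*

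**What the plan says.** SAP section 8 sends these dates to an appendix: "Missing and partial radiotherapy and surgery dates will be imputed using algorithm described in APPENDIX 2". Appendix 2 then has two parallel rules for start dates, one for procedures (radiotherapy) and one for surgeries recorded outside the prior-surgery page.

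- **Day missing.** If the therapy falls in the month of first dose, the first dose date is used. If month and year do not "match month and year of first dose date then impute as first day of that month and year", the 1st of the month is used.
- **Day and month missing.** For procedures: "If both day and month are missing, then impute as maximum between 01JAN of the year and date of the first dose". For on-treatment or subsequent surgeries: "If both day and month are missing then impute as maximum between 01JAN of the year and date of the first dose".

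First dose is the only date a start date is compared with. Death and last known alive date bound imputed end dates only.

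The imputed start then feeds the efficacy endpoints. Protocol 8.3.2 counts local therapy as a censoring therapy: patients treated before progression, "including tumor-directed radiotherapy and tumor-directed surgery, will have their PFS time censored on the date of their last tumor assessment prior to subsequent therapy". SAP 4.2.2.1 applies the rule: "Subjects who receive subsequent anti-cancer therapy prior to documented progression will be censored at the date of the last evaluable tumor assessment" on or before the start of that therapy. The footnote to Table 4.2.2.1-1 adds: "Tumor assessments and death if any, occurring after start of subsequent anti-cancer therapy are not considered". The table keeps a progression as an event if it is dated before, or on the day of, the start of therapy. SAP 4.2.4 censors DOR at the last evaluable scan before subsequent therapy, and SAP 4.2.3 closes the best-response window at subsequent therapy.

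**The concern.** The usual order is progression first, local therapy second. Protocol 3.4.3 asks for an evaluation for objective progression before palliative radiotherapy, and Protocol 3.4.1 takes patients who need non-palliative radiotherapy or surgery off study treatment. Imputing to the earliest possible day tends to reverse that order on paper. The progression is then dated after the start of therapy and drops out of primary-definition PFS, and the patient is censored at an earlier scan or at randomization.

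That censoring is informative, because only patients with an observed progression can lose an event this way. Kaplan-Meier curves for PFS and DOR would tend to lie too high. Response moves the other way: an earlier cut-off can only remove a CR or PR from the best-response window.

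**Working it through.** The plan gives no figure on this point, so the check applies its rules to dated records and then to simulated ones.

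**Rule as coded.** Let R be randomization, F first dose, P documented progression and S* the imputed start of therapy.

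- Day missing: S* = F if the therapy is in the month of F, otherwise the 1st of the month.
- Day and month missing: S* = max(01JAN, F).
- If S* ≥ P, the event is kept and time = P − R + 1 (SAP section 8 duration convention).
- If S* < P, the patient is censored at C, the last on-study scan on or before S*, or R if there is none. Time = C − R + 1.

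**Dated records** (scans every 6 weeks from first dose)

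| Record | Recorded start | S* | Result |
|---|---|---|---|
| A: R 12 Feb 2018, F 14 Feb 2018, P 20 Jun 2018, therapy 4 Jul 2018 | full date | 4 Jul 2018 | event, day 129 |
| A | day missing | 1 Jul 2018 | event, day 129 |
| A | year only | 14 Feb 2018 | censored, day 1 |
| B: as A, but therapy 27 Jun 2018 | day missing | 1 Jun 2018 | censored at 9 May scan, day 87 |
| C: as A, but P 28 Mar 2018, therapy 31 Mar 2018 | day missing | 1 Mar 2018 | censored, day 1 (full date: event, day 45) |
| D: R 6 Nov 2017, F 8 Nov 2017, P 25 Apr 2018, therapy 9 May 2018 | year only | 1 Jan 2018 | censored at 20 Dec 2017 scan, day 45 (full date: event, day 171) |

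Record B is the usual pattern for a missing day: 129 − 87 = 42 days, one scan interval. Record D shows that a year-only date does not always go back to day 1, because a scan before 01JAN still counts.

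**Simulation.** There were 20,000 progressors per setting, all with a partial date and all with therapy truly after a scan-documented progression. Assumptions: exponential PFS with median 3.4 or 5.0 months (from another first-line trial cited in Protocol 1.2.2), uniform 26-month accrual, first dose within 3 days of randomization, scans every 6 weeks to week 48 and then every 12, and an exponential gap from progression to therapy.

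| Median PFS (months) | Mean gap (days) | Day missing: converted / at day 1 (% of all) | Mean shift if converted (days) | Day and month missing: converted / at day 1 (% of all) | Mean shift if converted (days) |
|---|---|---|---|---|---|
| 3.4 | 14 | 54.6 / 13.6 | 46.6 | 96.0 / 65.1 | 117.8 |
| 3.4 | 30 | 34.4 / 8.5 | 46.8 | 91.5 / 61.5 | 114.8 |
| 3.4 | 60 | 19.8 / 4.9 | 46.9 | 83.5 / 54.4 | 111.9 |
| 5.0 | 14 | 55.0 / 9.3 | 51.4 | 96.0 / 53.6 | 136.6 |
| 5.0 | 30 | 34.4 / 5.9 | 51.0 | 91.6 / 50.7 | 133.8 |
| 5.0 | 60 | 19.5 / 3.3 | 51.3 | 83.5 / 44.8 | 129.1 |

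Among converted year-only records, the share sent back to randomization runs from 44.8/83.5 = 54% to 65.1/96.0 = 68%. The rest lose only part of their PFS time.

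For comparison, the default in SAP section 8 for other partial dates (15th of the month, July 1) would convert about 6 to 19% with the day missing and 33 to 46% with day and month missing.

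**The case against.** The case for leaving the rule alone has weight.

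- **Reach.** Both primary endpoints and the only tested secondary endpoint are OS, which does not use these dates. Protocol 8.4.2.2 and SAP 7.5 rule out formal tests of PFS, ORR and DOR. Only radiotherapy and surgery follow Appendix 2; non-study medication has its own specification, which is not in the documents.
- **Built-in check.** PFS is also analysed irrespective of subsequent therapy (SAP 4.2.2.2 and 7.5.4), and that analysis is immune. SAP 7.5.4 tabulates censoring for subsequent therapy by arm and lists each patient under both definitions, so a converted progression can be found.
- **Frequency.** Survival contacts every 3 months also record subsequent therapy, so year-only dates may be uncommon, although no document gives a rate.
- **Defensible intent.** An early date is a cautious choice for a definition meant to exclude scans after new therapy. The surgery page also holds on-treatment procedures, and palliative radiotherapy is allowed on study, so first dose is the only floor valid for every record.

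All of this limits the size of the problem and the scope of the remedy. It does not remove the mechanism. The immune analysis leaves the primary-definition estimate uncorrected, and DOR has no counterpart that ignores subsequent therapy.

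A reader might also infer more than the documents support. They do not show that one arm gains, because nothing is said about partial dates or local therapy by arm. ORR is not inflated, since truncation can only lose responses. Nor does every year-only date lose the whole PFS time, as record D shows.

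**Conclusion.** The concern holds as a flaw in a stated rule, limited to untested secondary endpoints. A progression that preceded radiotherapy or surgery is lost from primary-definition PFS, and in the same way from DOR, whenever the imputed start falls before it. With a missing day the censoring usually falls about one scan interval early. With day and month missing it falls at randomization if no on-study scan precedes the imputed date, and otherwise at the last earlier scan.

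The conversion rates (20 to 55% and 84 to 96%) are conditional on a partial date, on therapy truly following progression, and on the simulation assumptions. The effect on the trial's estimates cannot be computed, because the number of partial dates is not given. It would be wrong to read this as a threat to the OS conclusions. It is a cheap improvement.

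**What to change.** Amend Appendix 2 for radiotherapy and surgery pages other than the prior-therapy pages:

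1. When only the day is missing and a documented BICR progression falls in that calendar month, impute the start to the progression date. Table 4.2.2.1-1 then keeps the event as a same-day progression. For therapies that truly followed progression this removes every day-missing conversion, since these arise only within the month of progression. State in SAP 4.2.4 that DOR treats same-day progression alike.
2. When day and month are missing and the therapy is recorded as given after study drug ended, use the later of 01JAN and last study dose date + 1. This limits day-1 censoring but may not restore the event. If record A had its last dose on 6 Jun 2018 (an assumed date), S* would be 7 Jun, with censoring at the 9 May scan: day 87 instead of day 1, but still not an event at day 129.
3. Otherwise keep the current rule and rely on the planned PFS analysis irrespective of subsequent therapy as the check.

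Step 1 should not be extended to year-only dates. If therapy truly began uniformly between first dose and progression (first dose uniform over a year, progression at one of scans 1 to 8), it would wrongly keep the event in about 74% of such records, with a median true gap of about 54 days.

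The cost is SAP wording and a few lines of derivation code, using data already collected. The downside of step 1 is that an event is occasionally kept when therapy truly began shortly before progression in the same month.

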# APPENDIX 3 IMMUNOGENICITY ANALYSIS: BACKGROUND AND RATIONALE

The following summary is from the FDA Guidance for Industry Immunogenicity Assessment for Therapeutic Protein Products and White Paper on Assessment and Reporting of the Clinical Immunogenicity of Therapeutic Proteins and Peptides – Harmonized Terminology and Tactical Recommendations by Shankar et al. The program-level definitions of sample- and subject-level ADA status are based on recommendation from the BMS Immunogenicity Council.

Immune responses to therapeutic protein products may pose problems for both patient safety and product efficacy. Immunologically based adverse events, such as anaphylaxis and infusion reactions, have caused termination of the development of therapeutic protein products or limited the use of otherwise effective therapies. Unwanted immune responses to therapeutic proteins may also neutralize the biological activity of therapeutic proteins and may result in adverse events not only by inhibiting the efficacy of the therapeutic protein product, but by cross-reacting to an endogenous protein counterpart, if present. Because most of the adverse effects resulting from elicitation of an immune response to a therapeutic protein product appear to be mediated by humoral mechanisms, circulating antibody has been the chief criterion for defining an immune response to this class of products.

ADA is defined as biologic drug-reactive antibody, including pre-existing host antibodies that are cross-reactive with the administered biologic drug (baseline ADA). Titer is a quasiquantitative expression of the level of ADA in a sample. By employing a serial dilution-based test method, titer is defined as the reciprocal of the highest dilution of the sample (e.g., dilution of 1/100 = 1/100 = 1/100). The ADA is also tested, via a cell-based biologic assay or a non cell-based competitive ligand-binding assay for a subpopulation of ADA known as neutralizing antibodies (NAb), which inhibits or reduces the pharmacological activity of the biologic drug molecule regardless of its in vivo clinical relevance. Non-neutralizing ADA (non-NAb) is ADA that binds to the biologic drug molecule but does not inhibits its pharmacological activity.

ADA should be tested using sensitive and valid methods and employing an appropriate strategy for elucidating immunogenicity. Detection of ADA is typically performed in three tiers (screening, confirmatory, and titer) using statistically determined cutpoints and samples testing positive in the ADA assay are analyzed for neutralizing activity, especially in late-stage clinical studies. "Detection" of ADA implies that drug-specific ADA was confirmed. The 'drug tolerance' of an assay (highest drug concentration that does not interfere in the ADA detection method) is not an absolute value and differs between individuals due to the varying avidities of ADA immune responses. An ADA sampling strategy of collecting samples at times when the least drug concentration is anticipated (trough concentrations) can increase the likelihood of accurate ADA detection.

It is useful to present ADA results from clinical studies as (a) characteristics of the ADA immune response, (b) relationship of ADA with pharmacokinetics (PK) and, when relevant, pharmacodynamics (PD) biomarkers, and (c) relationship of ADA with clinical safety and efficacy.

Clinical consequences of ADA can range from no apparent clinical effect to lack of efficacy (primary treatment failure), loss of efficacy (secondary treatment failure) or heightened effect due to

altered exposure to the biologic drug, adverse drug reactions (administration-related systemic or site reactions), and severe adverse drug reactions (anaphylaxis and unique clinical problems associated with cross-reactivity and neutralization of endogenous molecules). Thus it becomes important to examine any associations between ADA or any of its attributes with the various clinical sequelae. The presence of ADA may or may not preclude the administration of drug to ADA-positive subjects because the outcome is dependent upon the magnitude of the impact of ADA on PK and PD. Hence, the relationship of ADA with PK/PD is an important additional consideration, but does not necessarily result in a clinically impactful consequence per se.

